**Table 3. Schedule of events**

Visit	Screen	Part A							Part B											
		1	2	3	4	5	6	7	8	9	10	11	12	13	14	15	16	17	18	19
Week	up to -4	0	1	2	3	4	8	11	12	16	20	24	28	32	36	40	44	48	51	52
Informed consent	x																			
Physical examination and medical history	x	x							x											x
Concomitant medications	x	x	x	x	x	x	x	x	x	x	x	x	x	x	x	x	x	x	x	x
Pregnancy test	x					x	x		x	x	x	x	x	x	x	x	x	x		x
Quantiferon test	x																			
Virology	x																			
ECG	x								x											x
Clazakizumab/placebo		x				x	x													
Clazakizumab									x	x	x	x	x	x	x	x	x	x		
Safety																				
AE monitoring		x	x	x	x	x	x	x	x	x	x	x	x	x	x	x	x	x	x	x
Safety Lab		x	x	x	x	x	x	x	x	x	x	x	x	x	x	x	x	x	x	x
LDL/HDL cholesterol, triglycerides		x	x	x	x	x	x	x	x	x	x	x	x	x	x	x	x	x	x	x
CMV PCR									x		x			x			x			x
Evaluation of PK																				
Clazakizumab concentration and anti-clazakizumab antibodies		x	x	x	x	x	x		x	x	x	x	x	x	x	x	x	x		x
Evaluation of PD																				
Ultrasensitive CRP		x	x	x	x	x	x	x	x	x	x	x	x	x	x	x	x	x	x	x
Preliminary efficacy assessment																				
Biopsies (incl. MMDx)								x											x	
DSA detection		x							x											x
Ig (sub)classes		x							x											x
Cytokine patterns		x							x											x
Endothelial markers		x							x											x
Leukocyte subpopulations		x							x											x
TTV copy number		x							x											x
eGFR		x	x	x	x	x	x	x	x	x	x	x	x	x	x	x	x	x	x	x
Protein/creatinine ratio		x	x	x	x	x	x	x	x	x	x	x	x	x	x	x	x	x	x	x
Liver metabolism																				
Pantoprazol i.v.		x							x											x
Pantoprazol concentration		x							x											x
Immunosuppression																				
CNI trough level		x	x	x	x	x	x	x	x	x	x	x	x	x	x	x	x	x	x	x
Biobanking		x							x											x

Long visits (approx. 6-9 hours) in grey

Primary outcome measures are the safety and tolerability of clazakizumab, evaluated throughout the study period (19 visits until EOS visit at 52 weeks). Secondary endpoints are pharmacokinetics (clazakizumab concentration) and pharmacodynamics (suppression of CRP). For preliminary efficacy assessment, blood-derived biomarkers of ABMR (HLA/DSA antibody levels, cytokines and markers of endothelial injury, patterns of peripheral blood leukocyte subpopulations) and IL-6/IL-6R gene expression will be assessed at day 0, and after 12 and 52 weeks. The study will include two protocol biopsies, an early biopsy after 11 weeks (end of part A) to primarily dissect the effect of IL-6 blockade on microcirculation inflammation in direct comparison to placebo, and a late biopsy after 51 weeks to assess the

effect of clazakizumab on the progression of chronic injury (cg score, IFTA score). All biopsies will in addition be evaluated for ABMR-typical gene expression patterns (ATAGC, Alberta University, Edmonton; major read-out: molecular ABMR score). We will in addition monitor kidney function, protein excretion and graft survival over the whole study period. Finally, we will assess the impact of IL-6 blockade (as compared to placebo) on pharmacokinetics of pantoprazole reflecting CYP-dependent liver metabolism. At day 0, week 12 and week 52, pantoprazole will be administered at a dosage of 20 mg intravenously, and drug levels will be determined every hour over a period of 6 hours. In patients on continuous proton pump inhibitor therapy, oral treatment will be paused for 3 days before pharmacokinetic testing, and re-started one day thereafter.

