**Clinical Pharmacology.** Following the administration of clazakizumab as a 1-hour IV infusion, the PK of clazakizumab were linear over the dose ranges of 30 mg to 640 mg in healthy subjects and 80 mg to 320 mg in subjects with RA as indicated by consistent clearance at these dose levels. The T-half of clazakizumab at all doses was very similar in healthy male subjects and in subjects with RA and was consistent with that expected for a humanized IgG1 antibody. Across the doses studied, the mean T-half of clazakizumab ranged from 19.5 to 31.0 days in healthy male subjects and from 26.4 to 30.9 days in subjects with RA. The T-half of clazakizumab after SC administration in healthy male subjects was similar to the IV administration. In a Phase 1 study comparing IV and SC dosing in healthy male subjects, the mean T-half of clazakizumab was 30.7 days after a single IV dose and 31.1 to 33.6 days after SC administration. The bioavailability of clazakizumab after SC administration was 60% of the IV formulation. As expected, Cmax was lower and Tmax was longer for the SC administration relative to IV administration. Population PK analysis of the data from clinical studies in RA, PsA and healthy subjects have indicated that body weight affects the PK of clazakizumab such that both clearance and central volume of distribution increase with increasing body weight. Therefore, heavier subjects will have lower drug exposure compared with less heavy subjects.

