## **3. STUDY DESIGN**

This bi-center study (MUW, Charité Berlin) is an investigator-driven pilot trial designed to assess the safety, tolerability, pharmacokinetics, pharmacodynamics and efficacy (preliminary assessment) of humanized anti-IL-6 monoclonal antibody clazakizumab in kidney transplant recipients with late ABMR. This study, a phase 2 trial, has two subsequent sub-parts, a randomized placebo-controlled trial (part A) of 12 weeks, where recipients are allocated to receive either clazakizumab (n=10) or placebo (n=10), followed by an open-label prospective study, where all 20 study patients will receive clazakizumab for a period of 40

weeks. In this second part, treatment will be offered to all subjects for two major reasons: (i) in a recent uncontrolled preliminary observational study, interference with IL-6/IL-6R blockade in ABMR patients using tocilizumab was reported to be safe and well tolerated, and first results have suggested stabilization of kidney function in many of the treated patients; (ii) two subsequent protocol biopsies planned in our trial, which are necessary for an in-depth analysis of the early and late effects of IL-6 blockade, would not be justified for long-term placebo treatment. After completion of part A, the randomization sequence will be unblinded for a first analysis of data. A simplified flow chart of the trial is shown in Figure 1:

Figure 1. Trial overview

**Part A:** Patients will be randomized to receive either clazakizumab (25 mg subcutaneous [SC] administration) or placebo (1:1 randomization) for a period of 12 weeks (administration of clazakizumab/placebo at day 0, and after 4 and 8 weeks). After 12 weeks, patients will be subjected to a first follow-up biopsy. Primary goals of this part of the trial are to assess the safety, pharmacokinetics and pharmacodynamics of a short course of treatment. Moreover, part A will allow for a first preliminary assessment of the impact of clazakizumab on ABMR-associated inflammation detected in peripheral blood and in the rejecting organ allograft, on the pharmacokinetics of pantoprazole as a probe drug to investigate influence of IL-6 blockade on cytochrome P450-dependent drug metabolism, and on the short-term course of DSA MFI and kidney allograft function (eGFR, urinary protein excretion). The randomization

sequence will be unblinded for a first data analysis after the last patient has completed the 12-week follow-up period.

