**Table 1. Inclusion and exclusion criteria**

INCLUSION CRITERIA
Voluntary written informed consent
Age >18 years
Functioning living or deceased donor allograft after ≥365 days post-transplantation
eGFR >30 ml/min/1.73 m 
Detection of HLA class I and/or II antigen-specific antibodies (performed and/or de novo DSA).
Acute/active or chronic/active ABMR (±C4d in PTC) according to Banff 2013/2015
Molecular ABMR score (ABMRpm) ≥0.2
EXCLUSION CRITERIA
Patients actively participating in another clinical trial
Age ≤18 years
Female subject is pregnant or lactating
Index biopsy results:
T-cell-mediated rejection classified Banff grade ≥I
De novo or recurrent severe thrombotic microangiopathy
Polyoma virus nephropathy
De novo or recurrent glomerulonephritis
Acute rejection treatment <3 month before screening
Acute deterioration of graft function (eGFR decline within 1-3 months >25%)
Nephrotic range proteinuria >3500 mg/g protein/creatinine ratio
Active viral, bacterial or fungal infection precluding intensified immunosuppression
Active malignant disease precluding intensified immunosuppressive therapy
Abnormal liver function tests (ALT, AST, bilirubin > 1.5 x upper limit of normal)
Other significant liver disease
Latent or active tuberculosis (positive QuantiFERON-TB-Gold test, Chest X-ray)
Administration of a live vaccine within 6 weeks of screening
Neutropenia (<1 G/L) or thrombocytopenia (<100 G/L)
History of gastrointestinal perforation, diverticulitis, or inflammatory bowel disease
Allergy against proton pump inhibitors
History of alcohol or illicit substance abuse
Serious medical or psychiatric illness likely to interfere with participation in the study

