#### **4. INTERVENTIONS**

##### **Treatment with clazakizumab/placebo:**

Clazakizumab or placebo will be administered as single SC injection of 1 mL each by blinded qualified study personnel during the double blind phase. All study drug administrations will be documented in the subject's source documents and in the CRF.

Clazakizumab will be supplied in single-dose vials (25 mg/mL) for injection and provided by Vitaeris Inc. The placebo medication will be administered with normal saline for injection (commercially available in country) and will be provided by the Investigator. Prepared syringes may be stored for up to 24 hours in a refrigerator, 2°C to 8°C, and up to 4 hours of the 24 hours may be at room temperature, 15°C to 25°C. The prepared syringes will be protected from light. Prior to administration, clazakizumab/placebo injection must reach room temperature by storing unrefrigerated for 30 to 60 minutes before use.

*Storage and Accountability.* Clazakizumab will be stored at -20°C or colder, with protection from light. Placebo will be stored at controlled room temperature and should not be frozen. Study product disposition and accountability will be documented on the subject level, whereby all study product dispositions will be listed (drug accountability log). In a stock record, overall bulk study product supplies and accountability will be recorded.

*The following medications are prohibited during the study:*

Rituximab, eculizumab, proteasome inhibitors, IVIG, plasma exchange or immunoadsorption, other investigational drugs/treatments including commercially available anti-IL-6/sIL-6R monoclonal antibody drugs such as tocilizumab (Actemra®).

*The following concomitant medications are permitted during the study:*

Calcineurin inhibitors (CNI, tacrolimus or cyclosporine A), mammalian target of rapamycin (mTOR) inhibitor (everolimus or rapamycin), Mycophenolate mofetil (MMF)/mycophenolate sodium; low dose corticosteroids (prednisolone  $\leq$  5mg/day)

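### Table 3 has no pregnancy test at week 0, so the first injection can rest on a screening test up to four weeks old

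*Combined protocol and SAP*

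**What the plan says.** Table 3 gives "Pregnancy test" its own row. It is marked at screening (up to week −4), at weeks 4 and 8, at every four-weekly visit from 12 to 48, and at week 52. The week 0 cell is empty. Study drug is given at weeks 0, 4 and 8 in part A and every four weeks from 12 to 48 in part B.

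Table 1 lists "Female subject is pregnant or lactating" as an exclusion but attaches no test and no date to it. Section 9 (Pregnancies and Women of Child Bearing Potential) forbids dosing a woman whose pregnancy is known and requires highly effective contraception. It also acknowledges that adequate controlled data in pregnancy do not exist. It sets no date for a test. Random allocation (Section 3) and Interventions (Section 4) do not mention one either.

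**The concern.** The schedule pairs a pregnancy test with every dose except the first. A patient randomised to placebo first receives clazakizumab at week 12, with a test at that visit. A patient randomised to clazakizumab first receives it at week 0, without one. The documents give no reason for the difference.

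The Section 9 ban works only if pregnancy status is known. At week 0 the latest scheduled information may be four weeks old. A woman who was pregnant but tested negative at screening, or who conceived before day 0, could be dosed in full compliance with the protocol, although pregnancy is an exclusion. The drug is long-acting and cannot be withdrawn once injected. Section 9 reports three pregnancies on clazakizumab, one ending in spontaneous abortion and two with unknown outcome, so human experience offers little reassurance.

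**Working it through.** **Schedule count.** The plan states no figure to reproduce, so the check is an alignment of Table 3. The week row, the test row and the two dosing rows each have 21 fields (a label and 20 columns), so the blank cell does not look like a shift in the extracted table. The part A dosing marks also agree with the text of Section 3.

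| Item | Weeks | Count |
|---|---|---|
| Dosing, part A | 0, 4, 8 | 3 |
| Dosing, part B | 12, 16, …, 48 | 10 |
| All dosing visits | | 3 + 10 = 13 |
| Dosing visits with a same-visit test | 4, 8, 12, …, 48 | 12 |
| Dosing visits without | 0 | 1 |

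The last scheduled test before the first injection is therefore the screening test, at most 4 × 7 = 28 days old.

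**Could Safety Lab cover it?** Safety Lab is marked at all 19 post-screening visits, including week 0, and its contents are not listed. It is also marked at all 13 post-screening visits where the pregnancy test has its own mark (12 dosing visits plus week 52). The table therefore appears to treat the two as separate items.

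**Drug remaining at the next scheduled test.** Inputs are from Section 1, Clinical Pharmacology. The half-lives were measured in healthy men, in a Phase 1 comparison of the two routes: "the mean T-half of clazakizumab was 30.7 days after a single IV dose and 31.1 to 33.6 days after SC administration". For subcutaneous uptake, that section gives this figure: "The bioavailability of clazakizumab after SC administration was 60% of the IV formulation". The dose is 25 mg. Assumptions: first-order elimination, absorption phase ignored, and healthy-male half-lives applied to female transplant recipients.

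- Share of absorbed dose = 2^(−t / half-life); share of injected dose = 0.60 × that; amount = 25 mg × 0.60 × that.
- t = 28 days: 2^(−28/31.1) = 0.536 and 2^(−28/33.6) = 0.561. That is 32 to 34% of the injected dose, or 8.0 to 8.4 mg.
- t = 84 days: 2^(−84/31.1) = 0.154 and 2^(−84/33.6) = 0.177. That is 9 to 11% of the injected dose, or 2.3 to 2.7 mg. This line holds only if dosing stops after week 0, as it would if the week-4 test were positive and acted on before the second injection.

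**Rough frequency.** The documents do not give the number of women of childbearing potential. Purely for illustration, assume 1 to 5 such women in the clazakizumab arm, a conception rate of 1 to 10% per year, and the full 28-day gap. Expected conceptions in the window are then 1 × 0.01 × 28/365 = 0.0008 to 5 × 0.10 × 28/365 = 0.04 for the whole trial. Pregnancies missed at screening are not counted here.

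**The case against.** The strongest objection is about weight. The number of women affected is unknown and could be zero, the illustrative frequency is far below one event, and the screening gap may be shorter than its maximum. The screening test, the exclusion criterion, the contraception rule, and the history and physical examination at week 0 all reduce the risk. This stands, with one qualification: the contraception rule is worded for women being treated, so its cover before day 0 is unclear.

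The residual-drug figures do not measure the harm of the missing test. A woman who conceived soon after a negative week-0 test would carry the same amount at week 4, and after later doses she would carry more. This also stands. The figures show only that an exposure at week 0 is not over by week 4; neither the finding nor the fix depends on them.

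A same-visit mark does not mean that the result is seen before the injection, and no available text requires that at any visit. So the contrast between 12 covered visits and one uncovered visit is weaker than the count suggests. That supports writing the result requirement into the fix.

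Finally, Safety Lab at week 0 might include a pregnancy test. The text neither says so nor rules it out, but the separate rows make it an unlikely reading. The contraception definition to which Section 9 refers is not in the available text, and nothing is inferred from its absence.

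**Conclusion.** The concern holds. One of 13 dosing visits has no same-visit pregnancy test, and it is the first exposure in the active arm. A first dose can be given on a test up to 28 days old, and one 25 mg dose precedes the next scheduled test.

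The practical risk is small and confined to women of childbearing potential among the 10 patients randomised to clazakizumab. The retained-placenta finding in monkeys arose at parturition and at 22 and 220 times the human dose, so it is not evidence of harm from a single early dose. The plan does not contradict itself, since Section 9 bars dosing only when pregnancy is known. Sample size, endpoints and error rates are untouched. It is a safety-schedule gap worth correcting because the correction is trivial. The conclusion rests on the blank cell, on no other available text requiring a test before the first injection, and on Safety Lab not including one.

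**What to change.** Mark the pregnancy test at visit 1 (week 0) in Table 3. Add a footnote requiring a negative result before the first injection in women of childbearing potential. All 13 dosing visits would then have a same-visit test. This closes the window between screening and day 0; it does not shorten the wait after a conception that follows any later monthly test.

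The cost is one cell, one footnote and one routine test per woman concerned. Blood is already drawn at week 0, and the visit is already long: for pantoprazole, "drug levels will be determined every hour over a period of 6 hours" (Section 5, text after Table 3). A short wait for the result need not waste drug, since "Prepared syringes may be stored for up to 24 hours in a refrigerator" (Section 4). Same-day turnaround of the test is an assumption; the documents do not state it.

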**Collection of biological material (outside routine monitoring).** Plasma (10 mL; cytokines, endothelial markers, TTV load), serum (10 mL; HLA antibodies, cytokines, endothelial markers), whole blood (10 mL; flow cytometry, RNA for gene expression analysis) and urine (10 mL) will be collected before study initiation (day 0), after 12 and after 52 weeks (3x25 mL peripheral blood). For pantoprazole kinetics, peripheral blood samples will be collected serially (6 x 5 mL per day) at day 0, week 12 and week 52, respectively. Finally, for measurement of clazakizumab concentrations and anti-clazakizumab reactivity, serum will be obtained at every study visit (5 mL peripheral blood per visit; total of 17 visits). Biological material will be aliquoted and stored for testing (clazakizumab concentration, anti-clazakizumab antibody detection, HLA antibody detection, detection of cytokines and endothelial markers, TTV quantification) at the Department of Clinical Pharmacology.

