## 7. SAMPLE SIZE AND STATISTICAL ANALYSIS

For this pilot study, no exact sample size estimation can be performed, because the effect size is unknown (there is no prior information to base a sample size on). The primary endpoint will be safety and tolerability. A preliminary assessment of efficacy outcomes in 20

kidney transplant recipients with late ABMR will provide first data on the effect of clazakizumab on clinical, morphological, immunological and molecular endpoints. The respective results (e.g. comparison between clazakizumab and placebo with respect to microcirculation inflammation and molecular rejection scores; course of chronic injury from 3 to 12 months), including an assessment of variability, can be expected to provide a valuable foundation of the design of future trials. Analyses will be conducted according to the intention-to-treat principle. Continuous data (e.g. group comparisons in part A for DSA-MFI, g+ptc score, IF/TA score, molecular ABMR score, eGFR and protein/creatinine ratio after 3 months) will be analysed using parametric and non-parametric (independent/dependent data) tests. These include the Mann Whitney U test or the t-test, as appropriate. Nominal data (e.g. occurrence of AEs in the two treatment groups in part A of the study) will be compared using the Fisher's exact test, when appropriate. Transplant and patient survival or AE (SAE)-free survival will be evaluated using Kaplan Meier analysis and the log rank test will be applied for group comparisons. For paired data (e.g. difference in IF/TA score between month 3 and month 12 in the overall cohort - part B), paired t test or Wilcoxon test will be used as appropriate. Analysis of pharmacokinetics of clazakizumab and pantoprazol will include a description of the time evolution of antibody/drug concentration. Elimination half-life, Tmax, Cmax, clearance and volume of distribution will be computed using standard software. For some study endpoints, data on variability and center (median) that can be expected also for the present study, are available from a recent interventional randomized controlled trial performed at our unit, which included a similar cohort of kidney transplant recipients diagnosed with late ABMR (BORTEJECT, NCT01873157; unpublished data; protocol described in: Eskandary et al., *Trials*. 2014 Apr 3;15:107). The respective data obtained in study groups are listed in the table below:

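### Six hourly pantoprazole draws leave the first hour after an intravenous dose unsampled, so Tmax and Cmax are missed and the size of a clearance difference can be distorted in either direction

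*Combined protocol and SAP*

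**What the plan says.** Section 5 (text after Table 3) sets the dose: "At day 0, week 12 and week 52, pantoprazole will be administered at a dosage of 20 mg intravenously". It then states that "drug levels will be determined every hour over a period of 6 hours". Section 6, under collection of biological material, gives the count: "peripheral blood samples will be collected serially (6 x 5 mL per day) at day 0, week 12 and week 52".

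Section 7 says of both clazakizumab and pantoprazole that "Elimination half-life, Tmax, Cmax, clearance and volume of distribution will be computed using standard software". The purpose, in section 5, is comparative: "we will assess the impact of IL-6 blockade (as compared to placebo) on pharmacokinetics of pantoprazole reflecting CYP-dependent liver metabolism". Table 2 lists pantoprazole PK at weeks 0, 12 and 52 as a secondary outcome.

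The documents do not state how long the dose takes to give, when the clock starts, whether one of the six samples is pre-dose, how AUC is calculated, what is done about the concentration at time zero, or whether a compartmental model will be fitted. Table 3 marks the test days only. No section adds an earlier sample.

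**The concern.** After an intravenous dose the peak comes at the end of dosing and the concentration falls fastest straight afterwards. A schedule with nothing between 0 and 1 h does not observe that part of the curve. Terminal half-life can still be estimated from the later points. Clearance is dose divided by total AUC, so it needs the missing piece, and volume is derived from clearance.

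Pantoprazole is the trial's means of judging how far IL-6 blockade alters CYP-dependent metabolism. The placebo contrast exists only in part A, with 10 patients per arm. Section 7 presents the pilot's results as a foundation for later trials. A distorted effect size would be carried into that planning.

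**Working it through.** **Reproducing the plan's count.** Hourly at 1, 2, 3, 4, 5 and 6 h is six draws, or 6 × 5 = 30 mL, which matches section 6. Sampling at 0–5 h also gives six. Sampling at 0–6 h would need seven and does not match. Neither six-draw schedule has a point strictly between 0 and 1 h. If the 0 h draw is pre-dose, the post-dose draws start at 1 h and the gap is unchanged.

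**Inputs.** From the documents: 20 mg IV, six draws, hourly. Everything else is assumed, because the documents give no pantoprazole kinetics: half-lives of 0.5–8 h, two-compartment parameters, and a true clearance ratio of 1.5.

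**First-hour share, one compartment.** Share of AUC before 1 h = 1 − 2^(−1/t½).

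| Assumed half-life (h) | 0.5 | 1 | 2 | 3 | 5 | 8 |
|---|---|---|---|---|---|---|
| AUC before 1 h | 75% | 50% | 29% | 21% | 13% | 8% |
| 1 h level as % of initial | 25% | 50% | 71% | 79% | 87% | 92% |

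**When there is no bias.** For a mono-exponential bolus, back-extrapolation gives C(1)²/C(2) = C(0) exactly, so AUC and the clearance ratio are correct (1.50).

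**One two-compartment bolus in full.** Take V1 = 7 L, Q = 8 L/h, V2 = 5 L and CL = 8 L/h.
- k10 = 8/7, k12 = 8/7, k21 = 8/5. The exponents are 3.338 and 0.548 per hour, so C(t) = 1.780·exp(−3.338t) + 1.077·exp(−0.548t) mg/L.
- C(0) = 20/7 = 2.857, C(1) = 0.686 and C(2) = 0.362. The true peak is 2.857/0.686 = 4.2 times the 1 h level.
- Back-extrapolated C(0) = 0.686²/0.362 = 1.30, against 2.857.
- First-hour AUC by log-trapezoid is (1.30 − 0.686)/ln(1.30/0.686) = 0.96. The true value is (1.780/3.338)(1 − 0.0355) + (1.077/0.548)(1 − 0.578) = 1.34, which is 54% of the total 20/8 = 2.5.
- Clearance then comes out as 9.41 instead of 8 (+18%). Repeating with CL = 12 gives 15.92 (+33%). The ratio reads as 15.92/9.41 = 1.69 when the truth is 12/8 = 1.5.

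**Other assumed profiles.** Same method: error-free bolus, log-trapezoid, log back-extrapolation where there is no 0 h sample, terminal slope from the last three points. True ratio 12/8 = 1.5. The 0–5 h column assumes the 0 h draw is immediately post-dose. The last two columns use post-dose draws at 0.25, 0.75, 1.5, 3 and 6 h, the sixth being pre-dose.

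| V1 / Q / V2 | 1–6 h | 0–5 h | Redistributed | Clearance error, redistributed, at 12 L/h |
|---|---|---|---|---|
| 7 / 60 / 5 | 1.52 | 1.42 | 1.52 | +3.6% |
| 7 / 30 / 5 | 1.54 | 1.42 | 1.53 | +4.9% |
| 7 / 8 / 5 | 1.69 | 1.45 | 1.51 | +1.0% |
| 7 / 2 / 5 | 1.66 | 1.47 | 1.49 | −0.4% |
| 8 / 3 / 4 | 1.65 | 1.48 | 1.49 | −0.9% |
| 5 / 15 / 8 | 1.69 | 1.39 | 1.55 | +7.6% |
| 6 / 6 / 6 | 1.81 | 1.45 | 1.51 | +0.4% |
| 4 / 20 / 8 | 1.65 | 1.35 | 1.58 | +14.4% |

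With base clearances of 3, 6 and 10 L/h in the last four profiles, the ranges widen to 1.52–1.95, 1.33–1.48 and 1.47–1.62. At 3 L/h with 8 / 3 / 4, the 1–6 h draws are marginally closer to the truth than the redistributed ones (1.52 against 1.47).

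**Other unstated choices, 1–6 h draws.** A 15-minute infusion analysed as a bolus gives 1.41–1.49 with one compartment and 1.48–1.85 with two. Software that sets C(0) = 0 gives 1.54–2.11.

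**Equal kinetics.** If both arms have the same profile, the ratio is 1.0 under every schedule.

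**Precision of the redistributed draws.** For one compartment with 15% error, fitting ln C on time gives SD(ln CL) ≈ 0.15·√[1/n + (t̄ − 1/k)²/Sxx], with k = ln 2/t½. For 1–6 h, n = 6, t̄ = 3.5 and Sxx = 17.5. For the redistributed draws, n = 5, t̄ = 2.3 and Sxx = 21.4. The SD is 0.096 against 0.073 at a half-life of 1 h, 0.065 against 0.070 at 2 h, and 0.068 against 0.094 at 3 h (0.072 against 0.097 by simulation).

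**The case against.** The size of the distortion depends entirely on kinetics that the documents do not give. With fast distribution the 1–6 h ratio is 1.52, which is hardly wrong. A reader might take 1.69 as the expected reading, or infer that hourly sampling always overestimates clearance. The documents support neither. The first comes from one assumed profile. The second reverses if a 0 h sample is drawn straight after dosing.

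A reader might also infer that the trial cannot tell whether IL-6 blockade changes CYP metabolism. That does not follow. Equal kinetics give a ratio of 1.0, and in every case modelled a real difference kept its direction. No decision in the plan turns on its size.

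Section 7 gives one parameter list for a subcutaneous antibody and an intravenous probe, so Tmax and Cmax may have been meant mainly for the antibody. No clearance ratio or lead pantoprazole parameter is named. The outcome is one of many secondary outcomes in a 20-patient safety pilot.

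Most of this stands, and it limits the size and grade of the point. It does not remove the gap. The list is applied to both drugs, and clearance and volume for pantoprazole need the first hour whatever was intended for Cmax.

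**Conclusion.** The point holds as a limited one. On the plan's own figures no draw lies inside the first hour. With 1–6 h draws, Tmax is 1 h for nearly everyone and Cmax is a 1 h level; across the assumed two-compartment profiles the true peak was 1.6 to 9.2 times that level. Clearance and volume lean on an unobserved AUC.

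The consequence is possible distortion of the size of a real difference, with direction and amount depending on unstated choices: about 1.5–1.8 for a true 1.5 with 1–6 h draws (1.95 in the most extreme case tried), and about 1.35–1.48 with 0–5 h draws including an immediate post-dose sample. These figures assume non-instantaneous distribution and the listed parameters. Without those assumptions, only the gap and the unspecified timing are established. It is a minor-to-moderate point on a secondary outcome.

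**What to change.** Keep six 5 mL draws within 6 h, but change their times in sections 5 and 6: one pre-dose, at least two in the first hour after the end of dosing, and the rest spread to 6 h (for example pre-dose, 0.25, 0.75, 1.5, 3 and 6 h). The pre-dose draw also checks that the 3-day pause of oral proton pump inhibitor left no drug on board, which 1–6 h draws cannot do.

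State the dose duration and clock start, and record actual sampling times. In section 7, fix the AUC method and the rule for the time-zero concentration, and name log clearance, compared between arms at week 12 with adjustment for week 0, as the pantoprazole comparison.

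The number of draws, blood volume and visit length do not change. The bias is reduced but not removed: in the tabulated profiles the ratio was 1.49–1.58 and clearance error reached about 14%. Precision falls if the half-life is 2 h or more and distribution is instantaneous, slightly at 2 h and more clearly at 3 h.

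If three extra draws per test day (3 × 5 = 15 mL) are acceptable, adding 5, 15 and 30 min to the 1–6 h series brought the ratio to 1.49–1.51 and clearance error to between −1.6% and +0.3% in the assumed two-compartment profiles.
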